10.2 Follow up of the patients retreat from the investigation clinic

In case Of break premature After The treatment with The device doctor, the investigations expected For there assessment from the safety they will be performed 7 days After the interruption. THE subjects they will be informed that participation in these investigations is voluntary. Furthermore, they can ask that from the moment of withdraw no more data is recorded.

10.3 Politics Of replacement of the subjects retreat

THE subjects That Yes they withdraw give it study Before from the execution from the procedure surgical or immediately after, i.e. before visit 2 (7 days after treatment) they may be replaced by new subjects who meet the inclusion/exclusion criteria. Those who withdraw give it study after visit 2 will be included in the analysis.

10.4 Conclusion anticipated of the investigation clinic

The sponsor has The right Of close this investigation clinic in any moment. The THERE IS And The AI they mustto be informed.

The investigation clinic can to be interrupted prematurely in the following cases:

- Self Yes verify events adverse/events adverse of the device Like this serious That The relationship risk-benefitNot And acceptable
- Self The number Of dropouts And Like this high That Not There Yes can realistically wait a correctcompletion of the investigation clinic.

If the sponsor or investigator decides to terminate the clinical investigation before it is completed, yes will inform each other in writing indicating the reasons for the early termination. In finishing the study, the sponsor and the investigator will ensure that adequate consideration is given to the protection of the subject's interests. The sponsor will inform the Competent Authorities and the CE. There documentation will be archived in Clinical Trial Masters File in Investigators Files.

11 Monitoring plan

The Monitor will contact and visit the investigator regularly and will be authorized, upon request, to have access to all source documents needed to verify entries in CRFs and other documents relating to the CIP, provided that the confidentiality of patient data is maintained in accordance with the local regulations. It will be the Monitor's responsibility to inspect the CRFs at regular intervals during the study, to verify adherence to the CIP and the completeness, consistency and accuracy of the data entered on of them. Monitoring standards require full verification of the presence of consent informed, adhesion to the criteria Of inclusion/exclusion, there documentation from the SAE/SADE And there

Documento Studio WOUND-H Valutazione prestazioni e sicurezza [acido ialuronico lineare per il trattamento delle ferite]	Codice NA-01-23	v. 2 del 26 giugno, 2023	
--	---------------------------	--------------------------	---

registration of the main efficacy, safety and tolerability endpoints. To be compliant with ISO 14155 standard requires at least 3 monitoring visits. A study start visit, a visit routine and a final visit after the last patient has finished the study. For the present study 8 monitoring visits are planned: an initial visit (centre opening), 6 routine visits and one final visit. Routine visits will be conducted once a month. 100% of the source data will be monitored by the monitor (which means 100% of Source Data Verification). Monitoring will come conducted according to SOPs and will provide an ISO 14155 compliant monitoring report afterwards each visit for the sponsor and investigator. Depending on the quality of the data, they may be necessary more visits Of monitoring a discretion of the sponsor.

12 Changes of the floor Of investigation clinic

The proposed changes to the clinical investigation plan be submitted to the Competent Authority (CA) and to Ethics Committee (EC) of reference. Substantial changes can only be implemented after Obtained the approval of AC/CE. The changes intended to eliminate an apparent immediate danger for subjects can be implemented before receiving AC/EC approval. However, in this case, approval must be obtained as soon as possible after implementation. It is forbidden to apply exceptions to this clinical investigation plan without prior authorization from the AC/EC. The deviations from the clinical investigation plan occurring for any reason must be reported immediately to the Responsible Scientific who will be able to to determine self to exclude The patient from the study.

13 Responsibility relative to the device

The device will be sent to the Villa Sofia Rehabilitation Care Home Pharmacy which will take care of check the good state of conservation of the device and store it in the conditions indicated by manufacturer. THE devices they will come delivered to the Responsible Scientific or his delegate That will provide to store them in the conditions indicated by the manufacturer. The Scientific Manager is responsible for storage and maintenance of devices. Access to the devices is permitted only to members of the team Of research And The withdraw Of Everything is fine device needs to to be annotated on the Device Log File reporting The first name of the member of the team, there date And The lot. THE devices expired or unused they will come retreat give it Sponsors.

14 Calculation from the dimension sample collection

The sample size was calculated based on estimates of possible improvement in the Clinical Healing score at the desaturation (18-20 days) respect at the baseline using the information obtained from the literature^{5,6,8,10,11,14}. Sample size estimates were calculate in terms Of a variable Of answer continues hypothesizing a distribution Not normal, The change of the Clinical Healing score at the desaturation with a effect size (dz) Of 0.5 And considering 80% power. With these assumptions, the minimum required sample size is 53 subjects per treatment group. Therefore, considering a dropout rate of 5%, it is necessary the recruitment of 112 subjects.

Documento Studio WOUND-H Valutazione prestazioni e sicurezza [acido ialuronico lineare per il trattamento delle ferite]	Codice NA-01-23		
v. 2 del 26 giugno, 2023			

15 Analyses statistics

the primary endpoint is the improvement in the Clinical Healing score at visit 3 compared to baseline (visit 1). Assuming that the average change in Clinical Healing score for each treatment is Like this represented: Prog = result of the Clinical Healing score at the visit 2; BAS = result of the Clinical Healing score at baseline, the null hypothesis is represented by Prog = BAS and the alternative one by Prog \neq BAS. Statistical tests (Mann-Whitney test) will be conducted at a significance level of 0.05 per show improvement in Clinical Healing score at visit 3. Secondary endpoints will be analyzed as follows: Clinical Healing score at visits 2 and 4 - Mann-Whitney tests conducted at significance level equal to 0.05; The pain perceived by the patient when changing the dressing visits 2, 3 and 4 - Mann-Whitney tests conducted at the significance level of 0.05; The percentage of patients with a completely healed wound at visit 4 - two proportion z tests conducted at the level of significance even to 0.05.

16 Timings

The study involves the recruitment of 112 patients, it is estimated that this number of patients will be recruited a time of approximately 8 months. Considering that the time required to complete the follow-up for each patient is 30 days the overall duration of the study is estimated from the first date visit of the first patient will be Of 10 months. There relation the final will be provided After 3 months from the conclusionof the study.

17 Publication of the results

Within one year of the end of the trial the results will be published by the sponsor in agreement with The investigators second the mode established in the convention Between the sponsor And The center experimental. The study data will be published in a scientific journal appropriate to the type of study And introduce yourself to congresses scientific. THE data of the investigation clinic they will be deposited at a bank data accessible to the public (e.g. clinicaltrial.gov). There confidentiality of the data of the participants will be Alwaysguaranteed.

18 Ethics And requirements legal

The investigator will present this CIP and any related documents provided to the subject (such as information used For obtain The consent informed) to a Committee Ethical to to the Authority Qualified. Approval from the committee and the AC must be obtained before commencing the investigation clinic And needs to to be documented.

Documento Studio WOUND-H Valutazione prestazioni e sicurezza [acido ialuronico lineare per il trattamento delle ferite]	Codice NA-01-23		
v. 2 del 26 giugno, 2023			

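### With 53 per group, the two-sided Mann-Whitney test in Section 15 has about 70% power at an effect size of 0.5, not the stated 80%

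*Combined protocol and SAP*

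**What the plan says.** Section 14 bases the sample size on the change in Clinical Healing score at suture removal. It does so "hypothesizing a distribution Not normal" and "with a effect size (dz) Of 0.5 And considering 80% power", and concludes: "With these assumptions, the minimum required sample size is 53 subjects per treatment group". Adding 5% for dropout gives 112 to recruit. No significance level and no number of sides appear in that section.

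Section 15 fills part of the gap. For the hypotheses, "the null hypothesis is represented by Prog = BAS and the alternative one by Prog \neq BAS". For the test, "Statistical tests (Mann-Whitney test) will be conducted at a significance level of 0.05". Section 5.5 gives 1:1 allocation. No section describes the primary test as one-sided.

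**The concern.** The number of patients, the effect size, the power and the test should fit together, and here they do not. A not-equal alternative tested at 0.05 is a two-sided test, and 53 per group looks too small for it at an effect size of 0.5. The symbol dz adds doubt, because it normally denotes a paired, within-patient effect size, whereas the sample size is given per treatment group.

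Two things are at stake. First, if the true effect is 0.5, the trial is more likely to miss it than Section 14 implies, and a null result would be reported against a power claim the design does not support. Second, while Section 14 is silent on sides, the choice between one-sided and two-sided 0.05 could be made after the data are seen. The false-positive rate in the favourable direction is 5% under the first and 2.5% under the second.

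**Working it through.** **Inputs.** Effect size 0.5, 80% power, 53 per group and 5% dropout (Section 14); Mann-Whitney test, 0.05 and a not-equal alternative (Section 15); 1:1 allocation (Section 5.5). One input is an assumption: Section 14 calls the distribution non-normal but names none. The main calculation uses the conventional Mann-Whitney efficiency relative to the t-test under a normal parent, 3/π = 0.955. Other parents follow below.

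**Method.** Find the per-group n for a two-sample t-test from the noncentral t distribution and divide by the relative efficiency. For power at a given n, set m = n × 0.955, with 2m − 2 degrees of freedom and noncentrality d√(m/2).

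**Reproducing the 53 (one-sided 0.05).** The t-test needs 50.15 per group, and 50.15 / 0.955 = 52.5, which rounds up to 53. Power at 53 is 80.3%. This matches Section 14.

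**The test as written (two-sided 0.05).** The t-test needs 63.77 per group, and 63.77 / 0.955 = 66.8, which rounds up to 67. At 53 per group, m = 53 × 0.955 = 50.6, the noncentrality is 0.5 × √(50.6/2) = 2.52 and the critical value is 1.98. Power is 70.2%. A simulation of 20,000 trials with a normal shift of 0.5 gave 70.7% two-sided and 80.8% one-sided at 53 per group, and 79.8% two-sided at 67.

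**Does another reading give 53?** Two-sided 0.05, d = 0.5:

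| Assumption | n per group for 80% | Power at 53 |
|---|---|---|
| t-test | 64 | 72% |
| Mann-Whitney, normal parent | 67 | 70% |
| Mann-Whitney, minimum efficiency 0.864 | 74 | 66% |
| Mann-Whitney, logistic parent | 59 | 76% |
| Mann-Whitney, Laplace parent | 43 | 88% (85% simulated) |

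Noether's formula gives 69. None of these is 53. Reading dz = 0.5 literally, as a paired effect at 80% power, gives 27 to 31 patients one-sided and 34 to 39 two-sided, across the paired t and signed-rank versions. The dz label does not explain 53 either.

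**Dropout.** 2 × 53 = 106, and 106 / 0.95 = 111.6, which rounds up to 112. This step is correct, so the gap lies in the power calculation.

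**Size of the shortfall.** Under the normal-parent assumption, 53 per group gives two-sided 80% power at d = 0.56. If all 112 patients completed (56 per group), power at d = 0.5 would be 73%. Two-sided 80% at d = 0.5 needs 2 × 67 = 134 evaluable, and 134 / 0.95 = 141.05, so 142 recruited.

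**The case against.** The strongest reply is that Section 15 does not clearly state a two-sided between-group test. Its not-equal sign belongs to a within-patient contrast of a follow-up score with baseline. The follow-up score is defined at visit 2, although the endpoint is at visit 3. The sentence that names the Mann-Whitney test speaks of showing improvement, which leans one way. This is fair as a description. However, the not-equal sign is the only formal statement of direction in the document, two-sided is the usual default, and nothing says one-sided. If one-sided was intended, Section 15 contradicts it, and the two sections still have to be reconciled.

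A second reply is that one-sidedness is inferred. It is: the match to 53 also relies on the normal-parent efficiency, and a one-sided test would need 46 under a logistic parent and 59 at minimum efficiency. A two-sided test with a relative efficiency of about 1.20 (63.77 / 53) would also return 53. The inference is therefore plausible but not documented. The shortfall does not depend on it.

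A third reply is that a heavy-tailed Laplace parent lifts two-sided power above 80%. That is true, but the plan names no such parent, it would have produced 43 rather than 53, and it is unlikely for a coarse score with levels 1 to 5. Simulated ordinal outcomes with three and five levels and a standardised difference of 0.5 gave about 72%.

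Finally, type I error under the two-sided test is unaffected. What is wrong is the power claim.

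**Conclusion.** The concern holds. For the test and alternative that Section 15 writes down, 53 per group has about 70% power at a between-group standardised difference of 0.5, not 80%. The range is 66% to 76% from minimum efficiency to a logistic parent. The risk of missing an effect of that size is about 30% rather than 20%.

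This rests on reading the not-equal sign as governing the primary test, on reading 0.5 as a between-group d, and on a parent distribution that is not markedly heavy-tailed. That 53 came from a one-sided calculation is the best explanation found, not something the plan states.

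A separate conditional point: Section 5.6 lists two primary endpoints, while Section 15 treats one as primary. The plan does not split alpha, but if it were split equally (0.025 each), power for this endpoint would be about 60%.

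**What to change.** Rewrite the power statement in Section 14 to match the test. Suggested text: with 53 evaluable patients per group, a two-sided Mann-Whitney test at 0.05 has about 70% power for a between-group standardised difference d = 0.5, and 80% power for d = 0.56, assuming the normal-parent relative efficiency of 3/π. Replace dz with d. In Section 15, write the hypothesis as a between-group comparison of the change from baseline to visit 3, and say that it is two-sided.

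Recruitment stays at 112, and neither the test nor the data collection changes. The cost is an amendment to wording and a less favourable stated power.

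If the sponsor does not want to accept 70%, there are two other consistent choices. One is to raise the target to 67 per group, about 142 recruited. The other is to prespecify and justify a one-sided 0.05 test in both sections before any outcome data are seen.

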The clinical benefits of the device are supported by substantial supporting scientific literature the use of hyaluronic acid-based devices to improve wound regeneration. For an analysis more detailed from the literature relevant see there Investigator Brochures.

4 Goals:

The primary objective of the study is to evaluate the safety and performance of a medical device Of Class IIB to basic Of acid hyaluronic lineare used In the treatment from the wounds post-surgery. The outcomes of the study are the improvement of wound healing assessed through the Clinical Healing

Documento Studio WOUND-H Valutazione prestazioni e sicurezza [acido ialuronico lineare per il trattamento delle ferite]	Codice NA-01-23	
v. 2 del 26 giugno, 2023		

score (score from 0 to 5), That includes there assessment Of: redness, edema,

Documento Studio WOUND-H Valutazione prestazioni e sicurezza [acido ialuronico lineare per il trattamento delle ferite]	Codice NA-01-23		
v. 2 del 26 giugno, 2023			

suppuration, healthy granulation tissue and signs of re-epithelization; the percentage of patients with wounds completely healed at day 30 post-treatment; the pain perceived by the patient when changing from the dressing; there frequency of events adverse.

Team Of operators involved in study

The team Of operators involved in study And Like this composed:

Scientific director and coordinator of the study: [name]

Members effective of the team: [name]

All members of the team are surgeons specializing in Physiatry belonging to the Operating Unit Simple Rehabilitation Nursing Home Villa Sofia. The CVs of the team members are available in attached hereto clinical protocol.

5 Drawing Of the Study

This is an interventional, single-center study. The aim of the study is to evaluate the safety and performance of a class IIB medical device based on linear hyaluronic acid in treatment from the wounds surgical.

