Patients who have undergone surgery for knee prosthesis implantation will be chosen hip and recruited based on the selection criteria described below. Patients will be randomized into two groups in which the control group will receive the normal standard therapies for the treatment of wound (typically cleaning and disinfection only) while the treated group will receive two applications daily use of the medical device. The following visits are scheduled for patients: screening (visit 0) to collect the patient's demographic and clinical data, compliance with the inclusion/exclusion criteria; Baseline (visit 1) evaluation of the wound through the Clinical Healing score and start of treatment; follow up 1 (visit 2 – 7 days of treatment) clinical evaluation of the wound, Clinical Healing score, pain assessment upon dressing change; follow up 2 (visit 3 – de-suturing of the wound (18-20 days Of treatment) assessment clinic, Clinical Healing scores, assessment ache to the exchange dressing; follow up 3 (visit 4 – 30 days of treatment) clinical evaluation, Clinical Healing scores, assessment ache to the exchange dressing, determination healing wound (self completely cured or not). A photographic documentation of the wound during the healing process will come collected at visits 1, 2, 3 and 4. For safety assessment all adverse events and events adverse serious they will come sign in And evaluated in relation to those to report from the literature scientific Fordevices similar doctors.

Documento Studio WOUND-H Valutazione prestazioni e sicurezza [acido ialuronico lineare per il trattamento delle ferite]	Codice NA-01-23		 NOVA ARGENTIA
v. 2 del 26 giugno, 2023			

Scheme of the Clinical Healing Score ¹²

Healing score	Wound characteristics
5 – excellent	All wound area is pink; no bleeding on palpation; no granulation tissue; no connective tissue at incision margin.
4 – very good	Less than one quarter of wound area is red, no bleeding on palpation, no granulation tissue; no connective tissue at incision margin.
3 – good	Less than half of the wound area is red; no bleeding on palpation; no granulation tissue; no connective tissue at incision margin.
2 – poor	More than half of the wound area is red; bleeding on palpation; granulation tissue evident; incision margin not epithelialised.

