1 – very poor	Two or more of the following features: More than half of the wound area is red; bleeding on palpation; granulation tissue evident; no epithelium at incision margin; infection present with suppuration.

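### Section 15 writes the primary hypothesis at the wrong visit and within patients, and makes no covariate use of the visit 1 score; restate it between arms and pre-specify a baseline-adjusted rank test

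*Combined protocol and SAP*

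**What the plan says.** Section 15 opens by stating that "the primary endpoint is the improvement in the Clinical Healing score at visit 3 compared to baseline (visit 1". Section 5.6 also lists improvement in the score at visit 3 as a primary endpoint, and section 14 bases the sample size on "The change of the Clinical Healing score at the desaturation with a effect size (dz) Of 0.5".

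The hypothesis in section 15 follows a different line. Prog is defined as the score at visit 2, BAS as the score at baseline, and "the null hypothesis is represented by Prog = BAS", with a two-sided alternative. The test sentence then reads "Statistical tests (Mann-Whitney test) will be conducted at a significance level of 0.05 per show improvement in Clinical Healing score at visit 3". It states neither which quantity is ranked nor which groups are compared. For the secondary endpoints the wording is "Clinical Healing score at visits 2 and 4 - Mann-Whitney tests conducted at significance level equal to 0.05", which drops the reference to improvement that section 5.6 attaches to those visits.

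The visit 1 score is available before treatment has had any effect. Section 5 schedules "Baseline (visit 1) evaluation of the wound through the Clinical Healing score and start of treatment" at the same visit. Neither section 14 nor section 15 names a covariate or stratification factor.

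**The concern.** There are two linked weaknesses.

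**Specification.** A null of equality between a follow-up score and baseline is a before-versus-after statement. It can be false in both arms simply because wounds heal, and it says nothing about the device. Mann-Whitney compares two independent groups, so the written null and the named test do not belong together. The null also sits at visit 2, while the endpoint and the test are at visit 3. An analyst has to repair the hypothesis before running anything.

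**Efficiency.** Subtracting the visit 1 score gives it a fixed weight of 1, and ignoring it gives it a weight of 0. The best weight depends on the baseline-to-visit 3 correlation and on the two SDs, none of which the documents give. A covariate model estimates the weight from the data. What is at stake is power in a trial of 106 evaluable patients, and freedom from a choice made after the data are seen.

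**Working it through.** **1. The plan's own figure.** Inputs from section 14: effect size 0.5, power 80%, 53 per group, 5% dropout, 112 in total. Section 14 labels the effect dz, a paired-data symbol. I read it as a between-arm standardised difference in change, because that reading reproduces 53. For a Mann-Whitney test with normal data, use an effective size m = n × 3/π per arm, noncentrality d√(m/2) and 2m − 2 degrees of freedom.

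- n = 53 gives m = 50.6 and noncentrality 0.5 × √(50.6/2) = 2.515.
- One-sided 0.05: power 80.3% (52 per arm: 79.6%), so 53 is reproduced.
- Two-sided 0.05, matching the alternative written in section 15: power 70.2%; 80% needs 67 per arm.
- Dropout: 106/0.95 = 111.6, so 112.

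**2. Formulas for the three analyses.** Set the visit 3 SD to 1, the visit 1 SD to q and the correlation to ρ. The same true effect, 0.5 SD on change, is used throughout.

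- SD of change: s = √(1 + q² − 2ρq).
- Change score: d = 0.5.
- Visit 3 score alone: d = 0.5s.
- Baseline-adjusted: d = 0.5s/√(1 − ρ²).

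Example, q = 1 and ρ = 0.5: s = 1, so d = 0.5 for the visit 3 score and 0.5/0.866 = 0.577 adjusted.

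**3. Power at 53 per arm, two-sided 0.05 (q and ρ are assumptions).**

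| q | Change | Visit 3 score, ρ 0.3/0.5/0.7 | Adjusted, ρ 0.3/0.5/0.7 |
|---|---|---|---|
| 0.5 | 70.2 | 68.0 / 57.8 / 45.5 | 72.1 / 70.2 / 73.5 |
| 0.75 | 70.2 | 74.8 / 61.2 / 43.0 | 78.6 / 73.6 / 70.4 |
| 1 | 70.2 | 83.8 / 70.2 / 48.8 | 87.1 / 82.0 / 77.1 |

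**4. Five-level scores.** The formulas assume normal data, so the comparison was simulated with a latent normal variable cut to levels 1-5. Assumptions: control arm at visit 3 10/20/30/25/15%, shift set so that the effect on change is 0.50 SD, 10,000 runs, simulation error about 0.45 points.

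| Visit 1 scores | Change, ρ 0.3/0.5/0.7 | Rank ANCOVA, ρ 0.3/0.5/0.7 | Gain |
|---|---|---|---|
| Bunched (q 0.45) | 71.9 / 71.4 / 71.1 | 74.0 / 72.0 / 72.2 | 2.1 / 0.6 / 1.1 |
| Intermediate (q 0.72) | 71.2 / 71.0 / 70.5 | 80.2 / 75.7 / 73.3 | 9.0 / 4.7 / 2.8 |
| Spread (q 1.01) | 70.0 / 69.8 / 70.3 | 90.2 / 86.0 / 82.2 | 20.2 / 16.2 / 11.9 |

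A separate simulation with other cut-points gave gains of about 0-2 points (bunched) and 8-19 (spread), with null rejection of 4.3-5.5%. Hence the quoted ranges of 0-2 and 8-20.

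**5. Where adjustment loses.** If improvement is independent of the visit 1 score, subtraction is already the right weight.

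- Symmetric visit 1 distributions over levels 1-3: change 71.4/71.1/70.9 against rank ANCOVA 70.2/69.3/69.7, a loss of 1.2-1.8.
- Visit 1 skewed to low scores (70/20/10% at levels 1-3): 73.5 against 71.1, and 74.0 against 69.9, a loss of 2.4-4.1. A repeat of these skewed cases gave 2.5-3.6.

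**6. Validity.** In the cases of steps 4 and 5 with symmetric baselines, null rejection was 4.7-5.4% for change and 4.7-5.5% for rank ANCOVA.

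**7. Effect estimate.** Without a covariate, the difference in mean ranks divided by N equals the probability that a device patient scores better than a control patient (ties counted half) minus 0.5. So 0.5 + arm coefficient/N is the adjusted form. Coverage of its 95% CI in the simulated cases with an effect was 94.4-95.8%.

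**The case against.** The strongest reply is that the intended variable is plain. The opening of section 15, its test sentence, section 14 and section 5.6 all speak of improvement or change. A reader might infer that the plan leaves the tested variable unnamed, but the documents do not support that. The raw-score reading rests on a shorthand line for secondary endpoints that section 5.6 itself defines as improvement. What stands is contradiction and imprecision, not absence.

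Second, a reader might take the gap between change and the raw score as the size of the problem. In one assumed case (visit 1 levels 45/10/45%, improvement independent of baseline) it is 70.9 − 32.6 = 38 points. Rank ANCOVA reaches 69.7 there, below change. That gap argues for stating that change is the variable, not for replacing the test.

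Third, the gain over change depends on assumptions and can be near zero or negative. This stands, and is why the gain is given as a range. Efficiency results for linear adjustment do not guarantee that rank ANCOVA never loses.

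Fourth, adjustment alters what is estimated, from improvement to the visit 3 score given the visit 1 score. This also stands, so sections 5.6 and 14 must be amended along with section 15.

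**Conclusion.** The concern holds as an inconsistent hypothesis together with an avoidable loss of efficiency. The visit 2 definition of Prog and the within-patient null conflict with a visit 3 endpoint tested by a two-sample test, and should be corrected whichever analysis is kept. A reader might infer that the planned test is invalid. It is not: Mann-Whitney on change, compared between randomised arms, holds its level.

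With 53 per arm, two-sided 0.05 and 0.5 SD on change, power for change is about 70%. Rank ANCOVA adds about 0-2 points with bunched visit 1 scores and about 8-20 with spread ones. The normal formulas at q = 0.5 and q = 1 give 0-3 and 7-17. The possible loss is about 1-4 points. All of this rests on assumed SDs, correlations and score distributions.

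Nor does adjustment by itself restore 80% power. With equal SDs, the formula reaches 80% at 53 per arm only for ρ of about 0.5 or lower, and in the bunched case power stays at 72-74%. The one-sided basis of the 53 is a separate matter. So are the missing section 15 test for wound size at visit 4 and the differing score ranges in sections 4 and 5.

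**What to change.** 1. In section 15, write the null between arms at visit 3, reconcile the visit 2 definition of Prog with the visit 3 endpoint, and name the variable tested.
2. Before outcome data are seen, pre-specify as primary a rank ANCOVA: ranks of the visit 3 score on arm and ranks of the visit 1 score. Report 0.5 + arm coefficient/N analysed, with its 95% CI, so that test and estimate come from one model. State in sections 5.6, 14 and 15 that the effect is the between-arm difference in visit 3 score given the visit 1 score. Keep Mann-Whitney on change as a sensitivity analysis.
3. Use the same method for the score at visits 2 and 4.

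If the sponsor prefers to keep change as the primary variable, item 1 is still needed.

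Cost: an amendment submitted to the Competent Authority and Ethics Committee under section 12, with approval before use if it is substantial. No new patients, visits or data are required. The statistical price is one degree of freedom and the possible loss of about 1-4 points noted above.
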